12.1.3 PK Analysis

The concentration of CVN424 in plasma will be summarized by dose over each scheduled sampling time using descriptive statistics. Individual plasma concentration data versus time will be presented in a data listing.

PK parameters of CVN424 will be derived using non-compartmental analysis methods from the concentration-time data for all subjects in the PK set. Actual sampling times, rather than scheduled sampling times, will be used in all computations involving sampling times. The following PK parameters will be determined from concentrations of CVN424 in plasma:

Symbol/Term	Definition
AUC_{∞}	Area under the plasma concentration-time curve from time 0 to infinity, calculated as $AUC_{\infty}=AUC_t+C_{last}/\lambda_z$, where C_{last} is the last quantifiable concentration.
AUC_6	Area under the plasma concentration-time curve from time 0 to 6 hours, calculated using the linear trapezoidal rule.
\mathbf{C}_{max}	Maximum observed concentration.
CL/F	Apparent clearance after extravascular administration, calculated as Dose/AUC $_{\infty}$ after a single dose.
λ_{z}	Terminal elimination rate constant, calculated as the negative of the slope of the log-linear regression of the natural logarithm concentration-time curve during the terminal phase.
$t_{1/2z}$	Terminal elimination half-life, calculated as $ln(2)/\lambda_z$.
t_{max}	Time to reach C_{max} .
V _z /F	Apparent volume of distribution during the terminal phase after extravascular administration, calculated as (CL/F)/ λ_z .

Additional plasma PK parameters may be calculated, including analyses by gender (if possible). Descriptive statistics (arithmetic mean, SD, median, minimum and maximum) will be used to summarize most plasma (PK) parameters for CVN424. Geometric mean and coefficient of variation will be computed for right-skewed measures, e.g., C_{max} and AUCs. Plots of C_{max} and AUCs versus doses will be generated.

Pharmacodynamic analyses will investigate the possible relationship between CVN424 PK parameters and efficacy and safety outcomes. Population analysis of results may be considered. Details of planned PK analyses will be presented in the SAP.

Study No. CVN424-201 Page 59 of 73

Protocol v. 4.0 14 July 2021

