PK parameters of CVN424 will be derived from the concentration-time data for evaluable subjects. The following PK parameters will be determined from concentrations of CVN424 in plasma: C_{min} at steady state (trough level on Day 22), C_{max} on Day 22, time to reach C_{max} on Day 22 (t_{max}), AUC from time 0 to 6 h (AUC₆), terminal elimination rate constant (λ_z), terminal elimination half-life ($t_{1/2z}$), apparent clearance (CL/F), and apparent volume of distribution (V_z /F).

- Pharmacogenomics:

One whole blood sample will be collected at Baseline for pharmacogenomic analysis; this will only be collected once per subject. A whole blood sample will be collected at pre-dose and 3 h post-dose on Day 1 for ribonucleic acid (RNA) pharmacogenomic analysis. The samples will be stored for no longer than 15 years after completion of the CVN424 study and/or until the drug development of CVN424 is no longer actively pursued by Cerevance or its collaborators. No samples will be stored for longer than permitted by the applicable law and samples will be destroyed upon notification from Cerevance. "Stored samples" in this context are defined as samples that are double coded (the samples are stripped of all personal identifying information but a key links the samples to the clinical data collected from the sample donor) and are used in the analysis of investigational drug or related drug.

The sampling of whole blood for pharmacogenomic and genotyping analysis is mandatory; every subject must sign the ICF in order to participate in this study. DNA samples can be used to identify markers (e.g., potential metabolites, or drug metabolic enzyme and transporter polymorphisms) that may contribute to variability in CVN424 PK, pharmacodynamics, or safety. Also, since pharmacogenomics is an evolving science, many genes and their functions are not yet fully understood. Future data may suggest a role of some of these genes in drug response, which may lead to additional hypothesis-generating exploratory research and diagnostic development on stored samples.

Endpoints:

The primary endpoint of this study will be:

Percentage of subjects with TEAE related to study drug

The secondary endpoints will include:

- Percentages of subjects with abnormal and clinically significant (CS) safety laboratory test results, ECG test results, or vital sign measurements at least once post-dose

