In the healthy volunteer study, CVN424 in suspension was rapidly absorbed after oral administration in the fasted state; peak plasma concentration was usually attained between 1 and 3 h post-dose (median 1.5 h). When CVN424 was administered after a meal, the peak plasma concentration was delayed and decreased while total exposure was minimally increased compared to the same dose level administered under fasted conditions. With repeated once-daily dosing, trough plasma concentrations usually reached a steady-state level by Day 4, with a terminal elimination half-life of approximately 33 h. Accordingly, CVN424 PK is appropriate for once-daily oral dosing, with or without food.

CVN424 is expected to be a pharmacological treatment for PD subjects, as monotherapy or adjunctive to dopaminergic therapy, to elicit sustained improvement of motor activity with a reduced risk of troublesome dyskinesia compared with dopaminergic therapies. As a novel, first in class, non-dopaminergic drug for the symptomatic treatment of PD, CVN424 may become a significant addition to neurologists' clinical armamentarium.

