9.1.13 PK Sample Collection

9.1.13.1 Collection of Blood for PK Sampling

Blood samples (one sample per scheduled time) for analysis of CVN424 plasma concentrations will be collected into chilled Vacutainers containing K₂EDTA according to the schedules in Table 5 and Appendix A.

Instructions for sample processing and shipment are provided in a separate lab manual.

Serial blood samples for determination of CVN424 concentrations in plasma will be collected according to Table 5.

 Table 5
 Collection of Blood Plasma Samples for PK Analysis

Study Day	Time Post-dose (hours).
1, 8	Pre-dose and at 3 h post-dose
15, 27	Post-dose (time not specified)
22	Pre-dose and at 1, 1.5, 2, 4, and 6 h post-dose
35	Washout (time not specified)

The PK samples will be collected at the nominal time point within the allowable windows per Table 8. The actual time of sample collection will be recorded on the source document and eCRF.

Placebo samples will not be analyzed by the bioanalytical laboratory except 2 samples per subject receiving placebo, 1 following first-dose (i.e., 3 h post-dose) and 1 at the Day 27 visit to ensure from a safety perspective that no additional subjects could have been on active treatment.

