9.1.14 PK Parameters

PK parameters of CVN424 will be derived using non-compartmental analysis methods from the concentration-time data for all evaluable subjects. Actual sampling times, rather than scheduled sampling times, will be used in all computations involving sampling times. The following PK parameters (Table 6) will be determined from concentrations of CVN424 in plasma:

Study No. CVN424-201 Page 41 of 73

Protocol v. 4.0 14 July 2021

Table 6	Pharmacokin	etic Parameters
---------	-------------	-----------------

Symbol/Term	Definition
AUC_∞	Area under the plasma concentration-time curve from time 0 to infinity, calculated as $AUC_{\infty}=AUC_t+C_{last}/\lambda_z$, where C_{last} is the last quantifiable concentration.
AUC ₆	Area under the plasma concentration-time curve from time 0 to 24 hours, calculated using the linear trapezoidal rule.
C_{max}	Maximum observed concentration.
CL/F	Apparent clearance after extravascular administration, calculated as Dose/AUC $_{\infty}$ after a single dose.
λ_{z}	Terminal elimination rate constant, calculated as the negative of the slope of the log-linear regression of the natural logarithm concentration-time curve during the terminal phase.
$t_{1/2z}$	Terminal elimination half-life, calculated as $ln(2)/\lambda_z$.
t_{max}	Time to reach C_{max} .
V_z/F	Apparent volume of distribution during the terminal phase after extravascular administration, calculated as (CL/F)/ λ_z .

Additional plasma PK parameters may be calculated, including analyses by gender (if possible).

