9.2 Monitoring Subject Treatment Compliance

Study medication will first be administered (on Day 1) while subjects are under observation at the investigative site. Subsequent doses will be self-administered at home, or at the investigative site on selected Study Visit days. The date and time of each observed dose will be recorded in the source documents and on the eCRFs.

At each weekly visit, subjects will return to the site all study medication bottles, whether empty or full, for assessment of treatment compliance.

An inventory of the study medication supplies dispensed will be performed by the site pharmacist or authorized study designee and recorded onto the Drug Accountability Log in the subject's source document records or equivalent.

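### CL/F and Vz/F are defined from a single-dose AUC-infinity that the planned sampling cannot provide, and Table 6 gives AUC6 the wrong interval

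*Combined protocol and SAP*

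**What the plan says.** Section 12.1.3 and Table 6 in Section 9.1.14 give the same definition of CL/F: "Apparent clearance after extravascular administration, calculated as Dose/AUC", where the AUC runs to infinity and follows a single dose. AUC-infinity is AUCt plus Clast/lambda-z, and Vz/F is CL/F divided by lambda-z. The method is non-compartmental. The synopsis (Section 2.0) lists "apparent clearance (CL/F), and apparent volume of distribution" among the parameters that will be determined.

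Table 5 (Section 9.1.13.1) sets the sampling:
- Days 1 and 8: "Pre-dose and at 3 h post-dose"
- Day 22: "Pre-dose and at 1, 1.5, 2, 4, and 6 h post-dose"
- Days 15, 27 and 35: one untimed sample each

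Table 6 defines AUC6 as "Area under the plasma concentration-time curve from time 0 to 24 hours, calculated using the linear trapezoidal rule". Section 12.1.3 defines it as "from time 0 to 6 hours, calculated using the linear trapezoidal rule", and the synopsis and the abbreviation list also say 6 h.

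Section 4.1 reports a "terminal elimination half-life of approximately 33 h". On dose times, Section 9.2 says: "The date and time of each observed dose will be recorded in the source documents and on the eCRFs". Section 6.1 names the observed doses as those on Days 1, 8 and 22.

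**The concern.** A single-dose AUC-infinity needs a post-dose profile long enough to fit a terminal slope. Day 1 is the only day on which a subject has had one dose, and it has one post-dose sample. Both active arms take 50 mg on Day 1 (Section 6.1), so 150 mg is never given as a first dose. Read literally, two listed parameters cannot be produced for any subject.

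An analyst holding the Day 22 profile might apply the formula there. By then subjects have dosed daily for about three weeks. The area from 0 to infinity therefore includes drug carried over from earlier doses, and dose divided by that area is not clearance. The protocol gives no steady-state formula and does not say which samples form the terminal phase.

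Multiple-dose PK is a secondary objective (Section 5.1.2), and Section 12.1.3 plans to relate PK parameters to efficacy and safety. The stake is PK reporting only, because plasma PK parameters are additional/exploratory endpoints (Section 5.2.3).

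**Working it through.** **Inputs from the plan.** Half-life about 33 h (Sections 4.1, 6.2); median tmax 1.5 h (Section 4.1); sampling times from Table 5; once-daily dosing.

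**The plan's own figure.** Section 6.2 says washout from Day 28 to Day 35 is about 5 half-lives: 7 × 24 / 33 = 5.09, which reproduces.

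**Day 1.** One post-dose point gives no slope. In a one-compartment model with tmax between 1 and 3 h, 0-3 h covers only 4.7% to 5.8% of single-dose AUC-infinity.

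**Day 22, stated formula, lambda-z at its 33 h value.** Assume one compartment with first-order absorption, and scale so that true Dose/CL = 1.
- k = ln 2 / 33 = 0.0210 per h; tmax 1.5 h gives ka = 3.415 per h.
- Accumulation R = 1/(1 − exp(−24k)) = 2.526. For assumed half-lives of 22 h and 40 h it is 1.885 and 2.939.
- ka·k/(ka − k) = 0.02113. C(6 h) = 0.02113 × 2.526 × exp(−6k) = 0.0471. Trough C(0) = 0.02113 × (2.526 − 1) = 0.0322.
- AUC6 by linear trapezoid at 0, 1, 1.5, 2, 4 and 6 h = 0.290.
- AUC-infinity = 0.290 + 0.0471/0.0210 = 2.530.
- CL/F ratio = 1/2.530 = 0.395. Extrapolated share = 1 − 0.290/2.530 = 88.5%. With lambda-z correct, Vz/F is low by the same factor.

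**Day 22, stated formula, lambda-z fitted to 2-6 h.** The grid has 45 two-compartment cases, all inputs assumed: distribution half-life 2, 3 or 4 h; 10% to 50% of AUC in that phase; ka 1.5, 2 or 3 per h; terminal half-life 33 h.
- Apparent half-life 2.95 to 16.9 h
- CL/F 0.653 to 1.387 of true
- Vz/F 0.118 to 0.335 of true
- With lambda-z held at its 33 h value in the same cases, CL/F is 0.308 to 0.386 of true

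**Noise in the slope.** The 2-6 h window is 4/33 = 0.12 half-lives, an 8% decline. With an assumed 10% residual CV, SE(lambda-z) = 0.10/√8 = 0.0354, or 168% of k. The fitted slope is then zero or positive in Φ(−0.0210/0.0354) = 28% of subjects.

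**Steady-state alternative.** AUC(0-24) = AUC6 + 18 × (C(6) + trough)/2 = 0.290 + 9 × (0.0471 + 0.0322) = 1.003 (unrounded inputs), so the CL/F ratio is 0.997. The result depends on how long before the trough the previous home dose was taken:

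| Gap before trough | One-compartment | Two-compartment range |
|---|---|---|
| 20 h | 0.937 | 0.832-0.922 |
| 24 h | 0.997 | 0.862-0.975 |
| 28 h | 1.058 | 0.885-1.030 |
| 48 h (dose missed) | 1.398 | 0.986-1.313 |

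**Half-life from Days 27 and 35.** Same clock time, 192 h apart, one compartment: 33.0 h if the last dose preceded the Day 27 sample. If a Day 28 dose fell in between and was ignored, the apparent value is 33 × 192/168 = 37.7 h (+14%).

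**The case against.** The strongest reply is that nothing tells the analyst to apply the formula to Day 22. The synopsis ties Cmin, Cmax and tmax to that day but not CL/F, and does not list AUC-infinity. On the plain reading the outcome is a parameter that cannot be reported, not a biased one. That is right, and the fold errors are conditional on the misapplication. They also come from noise-free profiles, and the two-compartment inputs have no source in the plan. With three noisy points the individual results would scatter far more.

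Section 12.1.3 defers PK detail to the SAP, allows additional parameters and says a population analysis may be considered. These routes could repair the problem. They are optional or unwritten, however, while the single-dose formula is stated twice, and the document supplied has no separate SAP text that replaces it.

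The reach is small. Cmin, Cmax, tmax and a 0-6 h AUC still serve the multiple-dose objective, and PK parameters are summarised descriptively. The AUC6 discrepancy is clerical.

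The proposed estimator interpolates across 18 unsampled hours and fails when the previous dose was missed. Dropping CL/F and Vz/F, or deriving them from a population model, would also remove the contradiction. Section 9.2 does not forbid recording home dose times; it only does not require it.

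**Conclusion.** The concern holds. As defined, CL/F and Vz/F cannot be obtained from the planned samples, and this follows from the text without any model. If the formula is applied to Day 22 instead, CL/F is about 2.5-fold low with a 33 h half-life (1.9- to 2.9-fold for assumed half-lives of 22 to 40 h). With lambda-z taken from 2-6 h it may err in either direction. Those sizes rest on linear kinetics, the one-compartment model or the assumed two-compartment grid, and no assay noise. AUC6 in Table 6 contradicts its symbol, the synopsis, the abbreviation list and Section 12.1.3, and sampling stops at 6 h. This should be corrected because it affects a secondary objective, but it does not touch the primary endpoint or the efficacy inference.

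**What to change.** In Table 6, Section 12.1.3 and the SAP:

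1. Define CL/F at steady state as Dose/AUC(0-24) on Day 22, built from the existing samples with the pre-dose trough as the 24 h value. State that it is approximate and assumes the trough is about 24 h after the previous dose. Say how subjects with a missed or mistimed previous dose are handled.
2. Drop AUC-infinity for Day 22.
3. Report lambda-z, half-life and Vz/F only where the Day 27 and Day 35 samples and recorded dose times support them. State which samples define the terminal phase and the rule for accepting a fit.
4. Record on the eCRF the time of the home dose before the Day 22 visit and of the last doses before the Day 27 and Day 35 samples, including any dose taken after the Day 27 sample.
5. Correct AUC6 in Table 6 to 0-6 h.

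The cost is wording plus a few recorded dose times, with no extra blood samples. Half-life and Vz/F will be available for fewer subjects, and CL/F will be approximate.

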12.1.4 Safety Analysis

12.1.4.1 AEs

All AEs will be coded by System Organ Class and Preferred Term using MedDRA. Treatment-emergent AEs with onset occurring within 30 days (onset date − last date of dose +1 ≤30) after study drug administration will be listed and included in the summary tables. Treatment-emergent AEs will be summarized by placebo, each CVN424 dose level and CVN424 overall by System Organ Class and Preferred Term. The following summary tables will be included in the report: summary of TEAEs and drug-related AEs, relationship of AEs to study drug (related vs not-related), severity of AEs and related AEs. AEs leading to study drug discontinuation and SAEs will be listed. Subgroup analyses will examine AEs among subjects categorized by selected demographic and disease characteristics. Data listings will be provided for all AEs including PTE, TEAEs, AEs leading to study drug discontinuation, and SAEs. All AEs will be listed.

12.1.4.2 Clinical Laboratory Evaluation

Individual results of laboratory tests from hematology, chemistry, urinalysis, and endocrine panels that are abnormal and CS will be summarized and listed. Observed values and change from baseline to post-dose laboratory data will be summarized for placebo, each CVN424 dose level and CVN424 overall. All clinical laboratory data will be listed.

12.1.4.3 Vital Signs

Individual results of vital signs that are abnormal and CS will be summarized and listed. Observed values and changes from Baseline in vital sign measurements will be summarized by placebo, each CVN424 dose level and CVN424 overall. All vital sign data will be provided in the data listings.

12.1.4.4 ECGs

Individual results of quantitative ECG parameters from the 12-lead safety ECGs that are abnormal and CS will be summarized and listed. Observed values and changes from baseline in quantitative ECG parameters will be summarized by placebo, each CVN424 dose level and CVN424 overall. Shift tables may be generated for the investigator's ECG interpretations that changed from baseline to the post-dose collections by above groups. All ECG data will be provided in the data listings.

12.1.4.5 Other Variables

Physical exam findings and suicidal assessments will be presented in data listings.

12.1.5 Efficacy Analysis

Serial assessments of average daily hours of OFF time as recorded in the Patient Motor Diary over the two days prior to each visit will be analyzed using mixed model for repeated measures (MMRM). The model will include fixed terms for treatment, visit, treatment x visit interaction and baseline measurement with subject-level unstructured covariance among repeated measurements. Other covariance structures may be used in case the model does not converge using unstructured

Study No. CVN424-201 Page 60 of 73

Protocol v. 4.0 14 July 2021

covariance structure. Additional covariates may be included based on review prior to breaking the blind. Two co-primary estimands of efficacy will estimate treatment-dependent difference in change from baseline to Day 27, one for each active dose vs. placebo, and will be tested using linear contrasts of least-square means. Each co-primary comparison will test for significance at one-tailed p < 0.1 to control the overall type 1 error rate at 20% based on Dunnett's method for comparing two treatments to the same control. Additional contrasts will be used to test for a dose-dependent effect of treatment and to estimate dosage-dependent differences in change from baseline at all other visits. Additional and exploratory efficacy endpoints will be analyzed in the same model and using the same estimands.

Responder analysis will ascertain the incidence of clinically significant improvement.

Subgroup analyses will ascertain the potential impact on efficacy of subgroup variables reflecting various demographic and disease-related characteristics.

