12.0 STATISTICAL METHODS

12.1 Statistical and Analytical Plans

A statistical analysis plan (SAP) will be prepared and finalized prior to unblinding of subjects' treatment assignment. This document will provide further details regarding the definition of analysis sets, analysis variables and analysis methodology to address all study objectives.

A targeted data review will be conducted prior to unblinding of subjects' treatment assignment. This review will assess the accuracy and completeness of the study database, subject evaluability, and appropriateness of the planned statistical methods.

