Appendix A: Schedule of Study Procedures

Visit Number	SCREE	NING	1	2	3	4	5	6	7	Early Term- ination
Study Day:	Days -28 to -1	Days -2 & -1	Day 0	Day 1	Day 8 ±2 days	Day 15 ±2 days	Day 22 ±2 days	Day 27 ±1 day	Day 35 ±2 days	
Informed consent	X (a)									
Inclusion/exclusion criteria	X									
Demographics	X (a)									
Medical history	X(a)									
Concurrent medical conditions	X (a)									
Medication history	X (a)									
Vital signs and weight (b)	X (a)		X	X	X	X	X	X	X	X
Physical examination	X (a)		X		X			X	X	X
Height and BMI	X (a)							X	X	X
Clinical laboratory tests (c)	X (a)		X	X	X			X	X	X
Screening laboratory tests (d)	X (a)									
Patient Motor Diary (Hauser diary) (e)	X	X				X		X		
Concomitant medications	X		X	X	X	X	X	X	X	X
ECG (f)	X (a)			X	X			X	X	X
Randomization			X							
Study drug dosing (g)				< -	-	-	-	->		
DNA sample collection (h)			X							
RNA collection (i)				X						
PK blood collection (j)				X	X (k)	X	X	X	X	X
PTE assessment (1)	X		X	X						
AE assessment (m)			X	X	X	X	X	X	X	X
Study drug accountability					X	X	X	X	X	X
Unified Parkinson's Disease Rating Scale (UPDRS)			X			X		X	X	X
CGI			X			X		X	X	X
PGI			X			X		X	X	X

Study No. CVN424-201 Page 70 of 73

Protocol v. 4.0 14 July 2021

Visit Number SCREENING		1	2	3	4	5	6	7		
Study Day:	Days -28 to -1	Days -2 & -1	Day 0	Day 1	Day 8 ±2 days	Day 15 ±2 days	Day 22 ±2 days	Day 27 ±1 day	Day 35 ±2 days	Early Term- ination
Epworth Sleepiness Scale			X			X		X	X	X
Questionnaire for Impulsive-Compulsive Disorders (QUIP)			X			X		X		X
Beck Depression Inventory			X					X		X

- (a) Initial Screening items, to be completed prior to other Screening assessments. Screening activities must occur within 28 days of randomization, but may be completed in fewer than 28 days. Screening days are nominally called Day -28 to Day -1, but will not necessarily correspond numerically to the calendar days prior to the Baseline Visit. By the same convention, the Patient Motor Diary will be recorded at home over 2 consecutive days during screening, but not necessarily on the 2 days immediately prior to the Baseline visit (Day 0).

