 - In advance of Study Visits on Day 15 and 27, subjects will complete Diary entries recording their capabilities, limitations and motor symptoms over the prior 2 days (e.g., Days 13 and 14, or Days 25 and 26).
- (f) Triplicate standard 12-lead ECG will be recorded at Screening and on Days 1 and 8 pre-dose [within 1 h prior to dosing] and 3 h (+/- 15 minutes) post-dose. Triplicate standard 12-lead ECG will also be recorded at screening and on Day 27, Day 35 and Early Termination (if applicable).
- (g) Upon randomization, the first dose of study drug will be administered under direction of site personnel. Near the conclusion of the Day 1 visit and subsequent weekly visits, subjects will be given a supply of study drug (as suspension in amber colored bottles) to be taken home and stored under refrigeration until use. Study drug will be self-administered each morning on days 2-28. However, for scheduled Study Visits on or around day 22, dosing must be deferred until after collection of a blood sample for determination of the study drug "trough" concentration.
- (h) One blood sample will be collected for pharmacogenomic analysis at baseline; this will only be collected once per

Study No. CVN424-201 Page 71 of 73

Protocol v. 4.0 14 July 2021

subject.

- (i) A whole blood sample will be collected pre-dose and 3 h post-dose on Day 1 for RNA pharmacogenomic analysis.
- (j) Blood samples for PK analyses will be collected at timepoints indicated in Table 5.
- (k) At Day 8 visit, one additional tube of blood plasma will be collected for archiving (frozen storage) to support potential post hoc laboratory testing (e.g., biomarkers, potential characterization of unknown CVN424 metabolites).
- (1) PTEs will be collected from signing of informed consent up until dosing on Day 1.
- (m) Any AE with onset or exacerbation after dosing on Day 1 will be captured as an AE.

Study No. CVN424-201 Page 72 of 73

Protocol v. 4.0 14 July 2021

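### The MMRM has no baseline-by-visit term, so the Day 27 OFF-time contrast can be slightly biased if the baseline slope changes between Days 15 and 27 and dropout also depends on baseline differently by arm

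*Combined protocol and SAP*

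**What the plan says.** Section 12.1.5 (Efficacy Analysis) gives the model: "The model will include fixed terms for treatment, visit, treatment x visit interaction and baseline measurement", with an unstructured within-subject covariance. The synopsis (section 2.0, Statistical Considerations) lists the same terms. The target is Day 27 alone: "Two co-primary estimands of efficacy will estimate treatment-dependent difference in change from baseline to Day 27, one for each active dose vs. placebo".

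Two post-baseline diary visits feed the OFF-time model. Appendix A, footnote (e), states: "In advance of Study Visits on Day 15 and 27, subjects will complete Diary entries recording their capabilities, limitations and motor symptoms over the prior" two days. The diary row of Appendix A has no mark in the Early Termination column, so a subject who drops out contributes at most a Day 15 value.

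Two clauses leave room for later detail. Section 12.1.5 adds: "Additional covariates may be included based on review prior to breaking the blind". Section 12.1 says: "A statistical analysis plan (SAP) will be prepared and finalized prior to unblinding of subjects' treatment assignment". Neither names a baseline-by-visit term. Section 12.1.5 also sends the additional and exploratory efficacy endpoints through the same model. Section 12.3 allows for 20% non-evaluable subjects and does not split that figure by arm or by baseline severity.

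**The concern.** The treatment effect may vary by visit and the residual covariance is unrestricted, but the baseline effect is held constant over time. The model therefore assumes that baseline OFF time predicts Day 15 and Day 27 equally. If the correlation with baseline weakens over time, that fails. With equal SDs at baseline and follow-up, the slope of change on baseline is the correlation minus 1, so assumed correlations of 0.6 at Day 15 and 0.5 at Day 27 would give slopes of -0.4 and -0.5. The Day 27 contrast would then be adjusted with a pooled slope instead of the Day 27 slope.

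This matters through missing data. An MMRM handles dropout that depends on baseline and the Day 15 value, provided the mean model is right. If the arms lose different baseline profiles and the slope is wrong at Day 27, part of that imbalance stays in the contrast, even though the covariate that explains the dropout is already in the model. What is at stake is the size and direction of the Day 27 estimates and, modestly, their error rate and power.

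**Working it through.** **1. The plan's own figure.** Inputs from section 12.3: effect 1.5 h, SD 3 h, one-sided 0.10, 45 per arm, 20% non-evaluable. Evaluable per arm: 45 x 0.8 = 36. Standard error: 3 x sqrt(2/36) = 0.707 h. Power by normal approximation: Phi(1.5/0.707 - 1.282) = 0.7995, which reproduces the stated 80%.

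**2. When the bias is zero.** For dropout after Day 15,

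bias = [(b27 - b) - g(b15 - b)] x D

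Here b15 and b27 are the true slopes of change on baseline, b is the fitted common slope, and g is the residual regression of Day 27 on Day 15. D is the difference, active minus placebo, in completers' mean baseline. If b15 = b27, then b equals both and the bracket is zero. If nobody drops out, or each arm loses the same baseline profile, D is zero in expectation. Both factors must be non-zero.

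**3. What the common slope is.** It is a GLS-weighted combination of the two visit slopes. With complete data and equal visit variances the weights are 0.50/0.50. With a variance ratio of 1.3 and correlation 0.6 they are 0.66/0.34. With a ratio of 2 and correlation 0.8 they are 1.18/-0.18.

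**4. Assumed inputs, none of them in the documents.** Baseline SD 2.5 h, visit correlation 0.6, dropout log-odds per baseline SD between 0 and +/-1.1, and about 17 to 23% missing at Day 27. The model was fitted by maximum likelihood to 400,000 simulated subjects per arm (Monte Carlo error about 0.01 h).

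| Slopes, Day 15 / Day 27 | Dropout | Bias, common slope |
|---|---|---|
| -0.4 / -0.4 | opposite by arm | 0 within error |
| different | unrelated to baseline, or same in both arms | 0 within error |
| -0.3 / -0.4 | differs by arm | 0.02 to 0.09 h |
| -0.3 / -0.5 | differs by arm | 0.05 to 0.17 h |
| -0.2 / -0.6 | differs by arm | 0.10 to 0.35 h |

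With baseline x visit added, the bias is at most 0.015 h in every scenario.

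**5. Hand check of the formula** (g taken as 0.6, loss after Day 15):
- Slopes -0.2/-0.6, higher-baseline patients leaving active only (0.7 per SD). The fitted b is -0.361 and D is -0.32 h. Bracket: -0.239 - 0.6 x 0.161 = -0.336. Bias: -0.336 x -0.32 = +0.107 h (simulated 0.108 h).
- Slopes -0.3/-0.5, opposite dropout of 1.1 per SD. The fitted b is -0.372 and D is -0.52 - 0.52 = -1.04 h. Bracket: -0.128 - 0.6 x 0.072 = -0.171. Bias: +0.178 h (simulated 0.171 h).
- Slopes reversed to -0.5/-0.3, active-only dropout as in the first check. The fitted b is -0.419 and D is -0.33 h. Bracket: 0.119 + 0.6 x 0.081 = 0.168. Bias: -0.055 h (simulated -0.044 h).

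A positive bias understates the reduction in OFF time, so it counts against the drug. The sign flips with the order of the slopes or with the dropout pattern.

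**6. At trial size** (45 per arm, 2,500 replicates):
- Slopes -0.3/-0.5, dropout unrelated to baseline: the SD of the contrast is 0.625 h with the common slope and 0.623 h with the extra term.
- Slopes -0.3/-0.5, opposite dropout of 0.7 per SD: bias about 0.10 h in either direction. The one-sided error in the drug's favour is 0.08 or 0.14, against about 0.11 with the extra term. Power is 0.84 or 0.90, against 0.87.
- Slopes -0.2/-0.6, opposite dropout of 1.1 per SD, in the direction unfavourable to the drug: bias 0.30 h, error in the drug's favour 0.04, power 0.71 against 0.85 with the extra term.

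**The case against.** The strongest reply is that similar slopes are the natural default. Regression toward the mean from a single screening filter shows up at the first re-measurement. Days 15 and 27 use the same two-day diary about 12 days apart. Section 4.1 reports that trough levels usually reach steady state by Day 4, and the high-dose step comes at Day 8. Slopes of -0.2/-0.6 would mean that carry-over of baseline falls from 80% to 40% in 12 days, which nothing in the documents suggests. This stands as a reason to expect a small bias. It does not justify fixing the slopes as equal when freeing them costs one parameter.

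A second reply is that the covariate clause and the later SAP provide a route. They do, but neither commits to the term, and a blinded review cannot see dropout that differs by arm. Whether the SAP adds the term cannot be told from the documents.

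A third reply is that OFF time is a secondary endpoint in a study whose primary endpoint is safety, with a planned overall type 1 error of 20%. That is right, and it keeps the priority low.

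A reader might also go further and infer that baseline-dependent dropout differing by arm is enough to bias the result. It is not: with equal slopes the bias is zero even under opposite dropout. Nor do the documents support reading the 20% allowance as expected differential dropout; it is a planning figure with no split.

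**Conclusion.** The point holds as a specification gap; no bias has been demonstrated. The Day 27 contrast is adjusted with a GLS-weighted slope pooled over Days 15 and 27, and it is biased only if the slopes differ and dropout depends on baseline differently by arm.

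Under the assumptions in the working, moderate scenarios give about 0.02 to 0.17 h, at most 0.17/1.5 = 11% of the target effect and 0.17/0.707 = 0.24 of the planning standard error. Only a strong slope change combined with strong opposite dropout reaches about 0.35 h (0.35/1.5 = 23% of the target).

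It would be tempting to read this as a route to a false positive. The most natural example, more severe patients leaving active drug while the slope steepens, biases against the drug. Inflation in the drug's favour needs the reverse dropout pattern or the reverse order of slopes. The documents give no slopes, baseline SD, visit correlation or dropout split, so neither the size nor the sign can be fixed from them.

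**What to change.** Name baseline x visit as a fixed effect in section 12.1.5, in the synopsis and in the SAP before unblinding, instead of relying on the open covariate clause. Apply it to OFF time and to the other endpoints analysed in the same model.

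The cost is one extra parameter for OFF time. UPDRS, CGI, PGI and the Epworth scale are also collected at Day 35. If that visit enters their models, which the text leaves open, the cost is one parameter more. The change touches protocol wording as well as the SAP. Sample size and stated power stay as they are, and the standard error is essentially unchanged.
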